Monocytes (relative)	Visit 4			normal/other than normal			normal/other than normal
ESR	Visit 0			normal/other than normal			normal/other than normal
ESR	Visit 2			normal/other than normal			normal/other than normal
ESR	Visit 4			normal/other than normal			normal/other than normal
Biochemical blood counts							
Urea	Visit 0			normal/other than normal			normal/other than normal
Urea	Visit 2			normal/other than normal			normal/other than normal
Urea	Visit 4			normal/other than normal			normal/other than normal
Creatinine	Visit 0			normal/other than normal			normal/other than normal
Creatinine	Visit 2			normal/other than normal			normal/other than normal
Creatinine	Visit 4			normal/other than normal			normal/other than normal

Version 1.0 of 12.11.2021

Protocol-Specific Version for Protocol #PHS-APIS-004-MEX-SOL-TAV. version 1.3 dated 07.06.2021

CONFIDENTIAL

page 39 of 58

Plan for statistical analysis of efficacy and safety parameters

Indicators	Stage	Investigational Products					
		Mexitol®			Placebo		
		W	P	Distribution	W	P	Distribution
Glucose	Visit 0			normal/other than normal			normal/other than normal
Glucose	Visit 2			normal/other than normal			normal/other than normal
Glucose	Visit 4			normal/other than normal			normal/other than normal
AST	Visit 0			normal/other than normal			normal/other than normal
AST	Visit 2			normal/other than normal			normal/other than normal
AST	Visit 4			normal/other than normal			normal/other than normal
ALT	Visit 0			normal/other than normal			normal/other than normal
ALT	Visit 2			normal/other than normal			normal/other than normal
ALT	Visit 4			normal/other than normal			normal/other than normal
Total protein	Visit 0			normal/other than normal			normal/other than normal
Total protein	Visit 2			normal/other than normal			normal/other than normal
Total protein	Visit 4			normal/other than normal			normal/other than normal
Total cholesterol	Visit 0			normal/other than normal			normal/other than normal
Total cholesterol	Visit 2			normal/other than normal			normal/other than normal
Total cholesterol	Visit 4			normal/other than normal			normal/other than normal
Triglycerides	Visit 0			normal/other than normal			normal/other than normal
Triglycerides	Visit 2			normal/other than normal			normal/other than normal
Triglycerides	Visit 4			normal/other than normal			normal/other than normal
Vital signs							
SBP	Visit 0			normal/other than normal			normal/other than normal
SBP	Visit 2			normal/other than normal			normal/other than normal
SBP	Visit 3			normal/other than normal			normal/other than normal

Version 1.0 of 12.11.2021

Protocol-Specific Version for Protocol #PHS-APIS-004-MEX-SOL-TAV. version 1.3 dated 07.06.2021

CONFIDENTIAL

page 40 of 58

Plan for statistical analysis of efficacy and safety parameters

Indicators	Stage	Investigational Products					
		Mexidol®			Placebo		
		W	P	Distribution	W	P	Distribution
SBP	Visit 4			normal/other than normal			normal/other than normal
DBD	Visit 0			normal/other than normal			normal/other than normal
DBD	Visit 2			normal/other than normal			normal/other than normal
DBD	Visit 3			normal/other than normal			normal/other than normal
DBD	Visit 4			normal/other than normal			normal/other than normal
HR	Visit 0			normal/other than normal			normal/other than normal
HR	Visit 2			normal/other than normal			normal/other than normal
HR	Visit 3			normal/other than normal			normal/other than normal
HR	Visit 4			normal/other than normal			normal/other than normal
RR	Visit 0			normal/other than normal			normal/other than normal
RR	Visit 2			normal/other than normal			normal/other than normal
RR	Visit 3			normal/other than normal			normal/other than normal
RR	Visit 4			normal/other than normal			normal/other than normal
Body temperature	Visit 0			normal/other than normal			normal/other than normal
Body temperature	Visit 2			normal/other than normal			normal/other than normal
Body temperature	Visit 3			normal/other than normal			normal/other than normal
Body temperature	Visit 4			normal/other than normal			normal/other than normal

Version 1.0 of 12.11.2021

Protocol-Specific Version for Protocol #PHS-APIS-004-MEX-SOL-TAV. version 1.3 dated 07.06.2021

CONFIDENTIAL

page 41 of 58

Plan for statistical analysis of efficacy and safety parameters

Table 3. Statistical analysis of the primary endpoint (template)

MRS scale scores	Mexidol®						Placebo							
	Visit 0	Visit 2	Dynamics to Visit 0		Visit 4	Dynamics to Visit 0		Visit 0	Visit 2	Dynamics to Visit 0		Visit 4	Dynamics to Visit 0	
			Abs.	%		Abs.	%			Abs.	%		Abs.	%
N														
Mean														
Median														
Min														
Max														
Qi														
Q3														
SD														
CV														
Comparison of drugs (statistical test ¹) (p-value)														
Indicator span diagram/ indicator scatter diagram or indicator trend diagram														

Table 4. Outcome of primary endpoint analysis (template)

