9.4. Dealing with dropped out, excluded patients and missing data

No missing data will be completed, missing data will not be taken into account when performing statistical analyses.

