All data obtained from the trial are subject to analysis. The final analysis of efficacy parameters will be performed after the clinical part of the trial is completed and the electronic database is finalised. If errors are identified in the electronic database prior to finalisation that cannot be resolved after the completion of patient participation in the trial, the statistical analysis of the data will include an analysis of the sensitivity of the resulting parameters to the presence of questionable data.

10. Safety analysis

Safety indicators as well as their changes will be presented using descriptive statistics by visit and therapy group. On trial visits, qualitative (dichotomous) measures will be compared between groups on the basis of Pearson's χ^2 test, if the frequency of a feature in at least one subgroup is 5 or less, Fisher's exact test (or Fisher-Freeman-Galton test for tables of arbitrary dimensionality).

The dynamics of quantitative safety indicators relative to baseline values will be evaluated and compared with each other using ANOVA analysis of variance with repeated measures. This method allows to simultaneously check the presence of statistically significant dynamics (at least one mean value in one time point differs from the rest), as well as to compare the dynamics and ranges of values of the indicator when receiving the compared preparations. In case of inappropriate use of parametric methods, similar analysis of changes in the distributions of

Version 1.0 of 12.11.2021

*Protocol-Specific Version for Protocol #PHS-
APIS-004-MEX-SOL-TAV. version 1.3 dated
07.06.2021*

CONFIDENTIAL

page 30 of 58

Plan for statistical analysis of efficacy and safety parameters

indicators during therapy will be carried out using non-parametric analogues - Friedman test and Wilcoxon sign rank test, and intergroup comparisons of changes - using the Wilcoxon-Mann-Whitney test.

The number and proportion of patients with reported adverse events after the first dose of the investigational product will be tabulated by therapeutic group. Descriptive statistics for adverse events will also be tabulated, taking into account severity, action taken and outcome.

The safety analyses will descriptively present the values of laboratory parameters as well as their changes from baseline values. In addition, clinically significant and nonsignificant deviations of laboratory values by visit will be tabulated by therapeutic group.

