Safety assessment will be carried out based on the analysis of the frequency of occurrence of all adverse events, dynamics of laboratory and instrumental parameters.

AEs are recorded after the first use of the drug until the patient completes the trial and are tracked throughout the trial until they are resolved/stabilised.

Frequency tables with data on discontinuation of therapy or changes in therapy parameters due to AEs will be presented.

Pre- and post-trial data will be compared to assess safety parameters.

All data will be analyzed on the safety population. Regardless of the reason for trial termination, data from all included patients will be included in the safety analyses of the trial therapy.

Adverse event (AE) is any adverse change in the health status of a patient or subject of a clinical trial to whom a medicinal (investigational) product has been administered, regardless of the causal relationship with its use.

Serious adverse event (SAE) - any adverse medical event that, regardless of the dose of the medicinal product, has resulted in death, is life threatening, requires hospitalization or its prolongation, has resulted in permanent or significant disability or impairment, is a congenital anomaly or birth defect or other medically significant event.

Adverse reaction (AR) - unintentional adverse body reaction associated with the use of a medicinal product/investigational product, suggesting at least a possible relationship with the use of a suspected medicinal product/investigational product.

Unexpected adverse reaction (UAE) - an adverse reaction, the nature, severity or outcome of which does not correspond to the information in the current instructions for medical use of the medicinal product or in the investigator's leaflet for an unregistered medicinal product.

Serious unexpected adverse reaction (SUAR) - an unexpected adverse reaction that is characterized by features of a SAE.

The parameters of the AE/SAE will be estimated as follows:

Severity of AEs:

The investigator assesses the severity of an adverse event according to the Common Terminology Criteria for Adverse Events (CTCAE) current version at the time of the trial. If an adverse event cannot be classified according to the CTCAE criteria, the Investigator will select the closest description of the severity of the adverse event from those given in the classification based on personal clinical experience:

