Clinical laboratory assessments will be presented with descriptive statistics by trial visit indicating changes from baseline. Laboratory abnormalities outside of normal values will be noted. Lists and summary descriptions of clinically significant haematological laboratory abnormalities will be presented. The feasibility of using a number of statistical methods will be assessed after data collection has been completed, as the nature of the data distribution, sample homogeneity, etc. is not known in advance. During the course of the analysis, the list of methods to be used may be modified and supplemented if necessary for the qualitative processing of the data. All deviations from the statistical plan of the survey as well as their causes will be detailed in the statistical report.

Based on the results of the trial, after the final statistical analysis, a conclusion will be made about the efficacy and safety of different dosages in sequential therapy with Mexidol® solution for intravenous and intramuscular administration, 50 mg/ml (RPC PHARMASOFT LLC, Russia) and Mexidol® FORTE 250 film-coated tablets, 250 mg (RPC PHARMASOFT LLC, Russia), vs. placebo. Table templates are provided in the annexes to this statistical plan.

11. Patient populations to be analysed

The following population groups will be used for the analyses:

- The ITT (Intent-to-treat) population will include all randomized patients regardless of investigational drug/placebo administration.
 - The mITT (modified Intent-to-treat) population will include patients who have completed the full course of therapy, regardless of the presence of Protocol violations/ deviations.
 - The PP (Per protocol) population will include patients who completed the trial in accordance with the Protocol.
- **Subpopulation of patients involved in the evaluation of the pharmacodynamic effects of the investigational therapy:** this population will include PP patients with relevant blood test results.

The primary population for the evaluation of efficacy criteria, proof of the hypothesis of

Version 1.0 of 12.11.2021

Plan for statistical analysis of efficacy and safety parameters

superiority of the investigational product therapy over placebo based on the primary efficacy criterion score, will be the PP population. Additionally, efficacy criteria will be analysed in the ITT and mITT populations. Safety parameters will be analysed in the ITT population.

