At the stage of statistical data processing, additional analyses of the efficacy and/or safety of investigational product/placebo in subpopulations of patients of different age groups can be performed.

The final report will include data on all patients included in the trial, including those who dropped out at any time without explanation. No missing data will be supplemented.

12. Interim analysis

The trial plans to conduct an interim analysis of the data, based on which a decision will be made whether to end the trial (if the trial objective is met) or to enroll the additional number of patients needed to confirm the efficacy of the drug, followed by pooling of all data for the final analysis. The choice of this approach is due to the change in the design of the planned clinical trial, duration of use and dosages of the investigational product compared to the previously conducted clinical trial (EPICA).

In the first phase, an interim analysis of the primary endpoint data will be performed on all randomized patients (304 patients) at the end of the trial:

- If the required power $\geq 80\%$ is achieved, a 95% one-sided confidence interval for the difference in values of the primary efficacy criterion ($\mu_t - \mu_p$) will be used to prove the hypothesis of 'superiority'; the results obtained will be analysed and used to write the final clinical trial report.

If the calculated power is less than 80 per cent, the sample size will be recalculated based on the data obtained after the first stage to achieve a trial power of 80 per cent, using a correction for genus I error α ($\alpha = 0.0294$). A protocol amendment will then be submitted to the Ministry of Health and, once approval is granted, the necessary additional number of patients will be enrolled, followed by pooling of all data for final analysis and writing of the final clinical trial report. A 97.06% one-sided confidence interval for the difference in values of the primary efficacy criterion ($\mu_t - \mu_p$) constructed from pooled patient data, i.e. obtained from the first and second stage results, using $\alpha = 0.0294$, will be used to prove the hypothesis of 'superiority'. The final clinical trial report will be written using data from all patients.

13. Table templates

Table 2. Results of assessment of normality of distribution of indicators (template)

Indicators	Stage	Investigational Products					
		Mexidol®			Placebo		
		W	P	Distribution	W	P	Distribution

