Plan for statistical analysis of efficacy and safety parameters

Table 7. Statistical analysis of pharmacodynamic effect indicators (template)

Indicator ⁸	Mexidol®						Placebo							
	Visit 1	Visit 2	Dynamics to Visit 0		Visit 4	Dynamics to Visit 0		Visit 1	Visit 2	Dynamics to Visit 0		Visit 4	Dynamics to Visit 0	
			Abs.	%		Abs.	%			Abs.	%		Abs.	%
N														
Mean														
Median														
Min														
Max														
Qi														
Q3														
SD														
CV														
Comparison of drugs (statistical test ⁹) (p-value)														
Indicator span diagram/ indicator scatter diagram or indicator trend diagram														

⁸ Indicators of LPO activity (malonic dialdehyde) and AOS indicators (superoxide dismutase, Se-dependent glutathione peroxidase), as well as indicators reflecting ED (Willebrandt factor, endothelin 1, homocysteine) and antihypoxant action (hypoxia-inducible factor HIF-1 α , lactate, neuron-specific enolase).

⁹ T-test for independent samples or Mann-Whitney test depending on the type of distribution of the indicator

Version 1.0 of 12.11.2021

Plan for statistical analysis of efficacy and safety parameters

Table 8. Statistical analysis of the proportion of disabled patients (template)

Percentage of disabled patients		Visit 2		Visit 4	
		Mexitol®	Placebo	Mexitol®	Placebo
Observed	Abs.				
	%				
Not observed	Abs.				
	%				
	%				
Comparison of groups (statistical criterion ¹⁰)					
p-level					

Table 9. Statistical analysis of safety indicators (quantitative data, template)

Safety indicator ¹¹	Mexitol®						Placebo			
	Visit 0	Visit 2	Visit 4	Dynamics to Visit 0		Visit 0	Visit 2	Visit 4	Dynamics to Visit 0	
				Abs.	%				Abs.	%
N										
Mean										
Median										
Min										
Max										
Qi										
Q3										
SD										
CV										
Comparison of drugs (statistical test ¹²) (p-value)										
Indicator span diagram/ indicator scatter diagram or indicator trend diagram										

Table 10. Statistical analysis of vital signs (quantitative data, template)

Safety	Mexitol®	Placebo
--------	----------	---------

¹⁰ Pearson 's χ^2 criterion or Fisher's exact test

¹¹ Clinical and biochemical blood counts.

¹² T-test for independent samples or Mann-Whitney test depending on the type of distribution of the indicator

Version 1.0 of 12.11.2021

Plan for statistical analysis of efficacy and safety parameters

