indicator ¹³	Visit 0	Visit 2	Visit 3	Visit 4	Dynamics to Visit 0		Visit 0	Visit 2	Visit 3	Visit 4	Dynamics to Visit 0	
					Abs.	%					Abs.	%
N												
Mean												
Median												
Min												
Max												
Qi												
Q3												
SD												
CV												
Comparison of drugs (statistical test ¹⁴) (p-value)												
Indicator span diagram/ indicator scatter diagram or indicator trend diagram												

Table 11. Safety performance assessment results: repeated measures analysis of variance (template)

Safety Indicator/Investigational Product	SS	DF	MS	F	p
Intercept					
Investigational Product					
Error					
Visit					
Visit*Dru					
Error					

Table 12. Results of safety indicators assessment: non-parametric repeated measures analysis of variance (Friedman test, template)

Investigational Product					
Indicator					
Visit	Average rank	Sum of ranks	Mean	SD	p
Visit 1					
...					

¹³ SBP, DBP, HR, RR, body temperature.

¹⁴ T-test for independent samples or Mann-Whitney test depending on the type of distribution of the indicator

Version 1.0 of 12.11.2021

**Plan for statistical analysis of efficacy and safety parameters***Table 13. Frequency analysis of safety performance outcome assessment (template)*

Investigational Product		Mexitol®			Placebo		
		Visit 0	Visit 2	Visit 4	Visit 0	Visit 2	Visit 4
Indicator 1							
Normal	Abs.						
	%						
Deviation	Abs.						
	%						
	%						
Comparison of groups (statistical criterion ¹⁵)							
p-level							
Indicator 2							
...							

Table 14. Frequency analysis of the safety outcome measure score (clinical significance, template)

Investigational Product		Mexitol®			Placebo		
		Visit 0	Visit 2	Visit 4	Visit 0	Visit 2	Visit 4
Indicator 1							
Deviation is clinically significant	Abs.						
	%						
Deviation is clinically insignificant	Abs.						
	%						
	%						
Comparison of groups (statistical criterion ¹⁶)							
p-level							
Indicator 2							

¹⁵ Pearson's χ^2 criterion or Fisher's exact test¹⁶ Pearson's χ^2 criterion or Fisher's exact test

Plan for statistical analysis of efficacy and safety parameters

Table 15. Statistical analysis of ECG (template)

Investigational Product		Mexidol®			Placebo		
		Visit 0	Visit 2	Visit 4	Visit 0	Visit 2	Visit 4
Normal	Abs.						
	%						
Deviation	Abs.						
	%						
	%						
Comparison of groups (statistical criterion ¹⁷)							
p-level							

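### The repeated-measures ANOVA for normally distributed safety indicators (SAP 10, Table 11) uses only patients with every visit; for vital signs it discards recorded Visit 2 values that a mixed model would keep (minor)

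*SAP*

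**What the plan says.** SAP 10 (Safety analysis) says that the course of quantitative safety indicators relative to baseline "will be evaluated and compared with each other using ANOVA analysis of variance with repeated measures". Table 11 lays this out with SS, DF, MS, F and p columns and rows for product, visit, product by visit and two error terms. Where parametric methods are unsuitable, SAP 10 uses Friedman and Wilcoxon signed-rank tests for change during therapy, and Wilcoxon-Mann-Whitney to compare changes between arms. SAP 9 makes Shapiro-Wilk the test that decides between the two routes.

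On missing values, SAP 11 states "No missing data will be supplemented", and protocol 9.4 adds that "missing data will not be taken into account when performing statistical analyses". On scope, SAP 10 states "Regardless of the reason for trial termination, data from all included patients will be included in the safety analyses of the trial therapy", and SAP 11 states "Safety parameters will be analysed in the ITT population".

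Protocol 8.2 and the schedule in Appendix 1 take vital signs at Visits 0, 2, 3 and 4, and blood and urine tests at Visits 0, 2 and 4. Under protocol 6.2, a patient who withdraws early has an end visit with the Visit 4 procedures. Neither document says which scheduled visit those readings belong to in the safety tables.

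**The concern.** A sums-of-squares repeated-measures ANOVA cannot use a patient who lacks a value at any visit in the table. With nothing filled in, that patient leaves the test entirely, including the values that were recorded. For vital signs the gap at Visit 3 decides the matter: even if the end-of-participation reading counts as Visit 4, nothing supplies Visit 3. For laboratory values the outcome depends on whether the end visit counts as Visit 4, which the SAP leaves open.

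Leaving need not be unrelated to safety. Protocol 5.3 lists adverse events that make continued participation dangerous among the reasons for exclusion. Visit 2 falls at the end of the intravenous course. The formal arm-by-time test could therefore omit the Visit 2 readings of patients who left for safety reasons, although those readings are in the database.

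**Working it through.** **Mechanism.** The documents give no complete-case rule; deletion follows from the named method plus no imputation. In a software check on simulated data with missed visits, a standard repeated-measures ANOVA routine stopped because the data were unbalanced and a Friedman routine returned no result. A mixed model used all 304 patients, of whom 277 were complete in that data set.

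**Number of patients.** The plan states no rate of missed safety visits, so the inputs are 304 randomized (protocol 9.1) and the earlier phase III trial's early dropout of 9 of 150 (protocol 2.3.2).
- Rate: 9/150 = 6%. Loss if every leaver goes between Visits 2 and 3: 304 x 0.06 = 18.
- At an assumed 10%: 304 x 0.10 = 30.
- The allowance of 304 - 228 = 76 (25%) in protocol 9.1 is not a dropout forecast. It also covers patients lost to the per-protocol set for other reasons.

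Patients who stay in the trial but skip Visit 3 would add to these counts; the documents give no rate for them.

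**Why the test can miss a signal in leavers.** If 10% of the active arm leave and only they are shifted, by 2 SD at Visit 2, the arm difference among all who attended Visit 2 is 0.10 x 2 = 0.20 SD. Among completers it is 0.

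**Power, like for like.** Both tests are the omnibus arm-by-visit test at two-sided 0.05, one on complete cases by ANOVA and one on all observed values by mixed model. Settings: 152 per arm, normal data at four visits, within-patient correlation 0.5 (assumed), equal shares leaving each arm after Visit 2, Visit 3 missing, and the end reading counted as Visit 4 with half of any leaver shift remaining. The mixed model's covariance is treated as known, which slightly favours it.

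| Scenario | ANOVA | Mixed model |
|---|---|---|
| 0.3 SD Visit 2 shift in all active patients, 6% leave | 75% | 77% |
| Same shift, 10% leave | 70% | 75% |
| Shift only in active-arm leavers: 6% leave, 1 SD | 5% | 7% |
| 6% leave, 2 SD | 5% | 13% |
| 10% leave, 2 SD | 6% | 27% |

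Repeat runs moved individual entries by up to about 3 points. In the last three rows the ANOVA rejects at about its false-positive rate. The shift sizes are assumptions; no document gives any.

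**The case against.** A reader might infer that the plan contradicts itself, because it promises all patients and then drops some. The documents do not support that. The statement in SAP 10 describes the safety analyses as a body, and SAP 11 names an analysis set; neither says that every test uses every patient. Early leavers remain, where data exist, in the by-visit summaries ("Safety indicators as well as their changes will be presented using descriptive statistics by visit and therapy group"), Tables 9-10 and 13-14, Mann-Whitney comparisons of changes, and the AE tables and listings.

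Nor is the loss hidden. Table 11 has a DF column, and Table 10 ("Statistical analysis of vital signs (quantitative data, template") has an N row for each visit. Safety conclusions rest mainly on adverse events (SAP 6), so a patient removed for a dangerous event is counted there. Indicators that fail Shapiro-Wilk go to Mann-Whitney on changes, which does not need every visit, and Friedman makes no between-arm comparison. The count of 18 is a worst case for timing: a patient who leaves before Visit 2 has no Visit 2 value to keep, and one who leaves after Visit 3 stays in if the end visit counts as Visit 4.

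A larger power gain can also be quoted: a baseline-adjusted contrast at Visit 2 alone stays at 85-86% for the common 0.3 SD shift. That is not a fair measure of the missing-data loss. With no loss at all the ANOVA reaches 77%, so much of the gap comes from setting a single contrast against a three-degree-of-freedom test.

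All of this stands, and it limits the point without removing it. SAP 9 and 10 allow methods to be supplemented after data collection, but that does not prespecify a remedy.

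**Conclusion.** The point holds and is minor. For vital signs judged normal, the planned arm-by-time test answers only for patients with all four visits and discards recorded Visit 2 values. Dropout would cost it at most 18 such patients at 6%, or 30 at 10%. The power lost is about 2 to 5 points for a shift common to the arm. It is negligible for small shifts confined to leavers (5% against 7%), and substantial only if the assumed shift is large (6% against 27%). These figures rest on the assumed correlation, shift sizes and timing of leaving.

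A reader might also infer that an effect at Visit 2 would go untested. That cannot be concluded. The between-arm comparison row in Tables 9-10 may cover Visit 2 values; the templates do not say. They show only one pair of change columns, placed after Visit 4. No particular drug effect at Visit 2 is claimed here.

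**What to change.** 1. In SAP 10 and Table 11, replace repeated-measures ANOVA with a mixed model for repeated measures on all observed post-baseline values, with arm, visit, arm by visit and baseline value. Report the arm difference and N at each visit.
2. Assign early-withdrawal readings to the nearest scheduled visit that has no reading yet.
3. Add a Visit 2 change-from-Visit-0 pair to Tables 9-10 and a Visit 3 pair to Table 10, each with a between-arm comparison.
4. Friedman (Table 12) may stay as a within-arm description, labelled complete-case with its N.

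The cost is SAP wording and a few template columns; the data are already collected. The downside is a few more safety comparisons to read.
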